3.1.1 Inclusion of Women and Minority

Women who meet the inclusion criteria, and have none of the exclusion criteria, will be enrolled without restriction as dictated by the study protocols. Because of the use of a study medication, woman of child bearing potential must meet specialized inclusion/exclusion criteria to minimize this risk. We will make efforts to enroll participants in this research in a distribution which mirrors the study population of the Pittsburgh area.

3.1.2 Inclusion of Children

This investigation will not enroll children based upon the target disease population and lack of safety data in adults.

3.2 INCLUSION CRITERIA

Potential study subjects must satisfy the following criteria to be enrolled in the study:

- Age 18-60 years old
- BMI ≥ 30 kg/m²
- Hypertension: defined as systolic blood pressure ≥ 130 and/or diastolic blood pressure ≥ 85 mm Hg at screening
- Waist circumference: >102 cm in men, >88 cm in women

The age and blood pressure criteria are specific to baseline screening at Visit 1. If subjects for instance have a birthday after Visit 1 or develop BPs outside of the screening criteria after drug dosing at Visit 4 or at subsequent visits, they will not be excluded. For safety purposes, subjects however can be excluded based on low mean arterial pressures (MAP) that persist on repeat PK testing on lower dose of study drug.

3.3 EXCLUSION CRITERIA

Subjects meeting any of the following exclusion criteria at baseline will be excluded from participating in the study:

- Positive urine pregnancy test or breastfeeding
- Recent addition or change in dosing of hormonal contraception medications (OCP, IUD, DepoProvera)
- Concurrent use of medications affecting glucose (oral hypoglycemics, insulin, atypical antipsychotics)
- Current use of ≥ 3 anti-hypertensive agents regardless of blood pressure control or normotensive (SBP <130 and DBP <85 mmHg) on a single agent
- Current use of PD5 inhibitors or organic nitrates
- Not stable on treatments for the prior three months or not planning to remain on current dose of medications for blood pressure, contraception, etc.
- Chronic psychiatric or medical conditions including diabetes, liver or kidney disease or obesity syndromes
- TSH >8 mIU/mL
- Smoker
- Hemoglobin <11 g/dL

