2. RESEARCH DESIGN AND METHODS

2.1 CLASSIFICATION AND METHODOLOGICAL DESIGNS

The study is a 12 week open-label, single-center, non-randomized drug treatment study of overweight adults with metabolic syndrome and hypertension.

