2.5 STUDY ENDPOINTS

2.5.1 Primary End-Points

Primary outcome measure: change in insulin sensitivity (ie. insulin stimulated glucose disposal) by hyperinsulinemic euglycemic clamp

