2.6 STATISTICAL ANALYSIS

Primary endpoint sample size estimates: To develop sample size estimates, we hypothesize that inorganic nitrite will have significant but perhaps slightly less robust effects compared to a 4-month supervised exercise weight loss intervention. We anticipate an effect size (improvement) in insulin stimulated glucose uptake of ~ 1.68 mg/min/kg fat free mass (FFM) with dietary nitrite. This represents just 60% of the effect size we have observed with diet and exercise (based on a mean

improvement in insulin sensitivity from 6.70 ± 2.0 (SD) to 9.51 ± 2.5 mg/min/kg FFM; n=25). This would provide 80% power to detect this conservatively-estimated smaller effect size in 30 subjects at a p value of 0.05.

Primary and secondary endpoint analyses: Repeated measures ANOVA with visit (pre-, post-treatment) as the within-subject effect will be used to evaluate response to treatment for primary and secondary endpoint measures of insulin sensitivity, mitochondrial function (muscle and platelet ROS generation, mitochondrial efficiency, and uncoupling by various platelet and muscle biopsy samples), BP, methemoglobin %, endothelial function (FMD), body weight, arterial stiffening (PWV), arterial thickening (IMT), glucose tolerance (HbA1C), blood markers of inflammation and vascular dysfunction, substrate oxidation (indirect calorimetry), cardiorespiratory fitness (maximal exercise tolerance test), and body composition (whole body DEXA for total body fat). Data will be presented as the mean \pm standard error for continuous variables. Transformations will be considered for data demonstrating non-normal distributions.

An interim statistical analysis is planned following completion of the 10th subject. If there is a statistically significant change in the primary outcome measure of insulin sensitivity with $p < 0.001$, discontinuation of the trial will occur. If $p > 0.001$, the trial will continue. Based on an extremely low p value to stop the trial, there will be no need to adjust final significance level.

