4. RECRUITMENT AND INFORMED CONSENT PROCEDURES

4.1 RECRUITMENT METHODS

The potential study subjects will be recruited from university and community advertisements and the University of Pittsburgh Nutrition and Obesity Research Center registry.

Potential subjects will also be identified by the physician investigator who is also the primary care or treating physician. The physician investigator who already has knowledge of and access to subjects' information will review the subjects' records to identify potential research subjects for

the study. After identifying potentially eligible subjects, the physician investigator will then approach these subjects to discuss the research opportunity.

To minimize the possibility that subjects will feel obligated to participate, investigators will reinforce with their subjects that participation is voluntary, that they do not have to participate, and the decision not to participate will not affect their care, now or in the future. The physician investigator will also allow subjects to make further inquiries if they are interested.

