5.1.2 Risk of Study Procedures

The collection of the research data from history and physical examination such as body weight, height and vital signs carries minimal risk. Intravenous blood sampling risks of bruising, infection, anemia, and fainting are common. The clamp study involves likely risk of discomfort associated from two venipunctures. The infusion of 20% sugar water during the clamp may cause local tissue damage if it leaks outside the vein. However, the chances for this happening are minimal because of very close observation by the nurse and doctor. Hematoma formation and hypoglycemia are rare complications, which we have not had since clamp experiments were initiated 16 years ago. The stable isotope glucose tracer in the amount used has no hazardous effects.

The risks of percutaneous muscle biopsy are bleeding and infection (both rare), bruising (infrequent) and discomfort (likely). With the use of a local anesthetic, our subjects describe the

discomfort of muscle biopsy as about twice that of intravenous cannulation. Some residual stiffness in the vastus lateralis can persist for 1-2 days (common). An elastic wrap and ice bag are applied post-biopsy to decrease the risk of bruising and for an anesthetic effect. In our experience using similar protocols, subjects have not experienced any adverse effects from these procedures other than a small amount of residual localized soreness at the biopsy site. Additional risk includes any unusual reaction to the elastic bandage wrap and ice, i.e. leg numbness which would indicate the elastic bandage had been applied too tightly or the ice left on too long; or any skin redness, irritation, and chafing from the applied antibiotic ointment and/or steri-strips.

The exercise test ($VO_2\max$) and subsequent exercise training sessions may cause muscle soreness or fatigue, but in adults without a known history of heart disease, the risk of heart attack or death from maximal or sub-maximal exercise bouts is rare. The relative risk of exercise testing for obese adults has not been clearly defined. However, a survey of more than 2,000 clinical exercise testing laboratories, in which more than 600,000 tests were performed, showed a death rate of approximately 1 per 20,000.

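### Entry criteria require stable medication but not stable weight, diet or exercise, so in this single-arm pre/post trial lifestyle change after the baseline clamp can bias the primary endpoint towards benefit

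*Combined protocol and SAP*

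**What the plan says.** Section 3.3 excludes subjects who are "Not stable on treatments for the prior three months or not planning to remain on current dose of medications for blood pressure, contraception, etc". The synopsis carries the same criterion. The rest of Sections 3.2 and 3.3 covers age, BMI, blood pressure, waist, pregnancy, contraception, medication classes, chronic conditions, TSH, smoking and hemoglobin. Nothing there concerns weight trend, dieting or training. The visit descriptions in Sections 2.3.1 and 2.3.2 do not ask subjects to hold diet or activity constant.

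On design, Section 2.1 states: "The study is a 12 week open-label, single-center, non-randomized drug treatment study". The endpoint in Section 2.5.1 is "Primary outcome measure: change in insulin sensitivity (ie. insulin stimulated glucose disposal) by hyperinsulinemic euglycemic clamp". Section 2.6 analyses it by repeated measures ANOVA with visit (before, after) as the only factor and no covariates.

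On the expected effect, Section 2.6 says: "We anticipate an effect size (improvement) in insulin stimulated glucose uptake of ~ 1.68 mg/min/kg fat free mass (FFM) with dietary nitrite". It adds: "This represents just 60% of the effect size we have observed with diet and exercise". The source data are given as "improvement in insulin sensitivity from 6.70 ± 2.0 (SD) to 9.51 ± 2.5 mg/min/kg FFM; n=25", from a 4-month supervised programme.

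Section 4.1 recruits from advertisements and from "the University of Pittsburgh Nutrition and Obesity Research Center registry". Section 5.1.2, describing the risks of the exercise test, continues: "and subsequent exercise training sessions may cause muscle soreness or fatigue". Neither Table 1 nor any visit description contains a training session.

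**The concern.** Section 1.3.1 itself names weight loss and exercise as effective treatments of insulin resistance, and Section 2.6 takes their effect as the yardstick for the drug effect. The factor most likely to imitate a nitrite response is therefore known and quantified in the protocol, yet entry does not control it and the analysis does not remove it. Without a concurrent control group, any gain from weight loss or training between the clamps at Visit 3 and Visit 18 adds directly to the estimated drug effect. Blood pressure, the first secondary endpoint, could plausibly shift with it.

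What is at stake is a positive primary result that partly reflects lifestyle change, in a trial whose result cannot be checked against untreated subjects.

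**Working it through.** **Inputs from Section 2.6.** Diet and exercise: 6.70 (SD 2.0) before, 9.51 (SD 2.5) after. Planned nitrite effect about 1.68. N = 30, 80% power, p = 0.05 (sidedness not stated; two-sided assumed). The pre-post correlation r is not stated; r = 0, 0.5 and 0.7 are assumed here.

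**The plan's own figure.** Gain = 9.51 − 6.70 = 2.81, and 0.6 × 2.81 = 1.686, which matches about 1.68. SD of change = √(2.0² + 2.5² − 2r × 2.0 × 2.5), which is 3.20, 2.29 and 1.80 for r = 0, 0.5 and 0.7. At r = 0 a two-sided paired t-test with 30 subjects has 79.3% power for 1.68 (82.0% by the normal approximation). The stated 80% is thus reproduced if zero correlation was assumed.

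**One subject.** A subject with the full gain exceeds the planned effect individually (2.81/1.68 = 1.67), but moves the mean of 30 by only 2.81/30 = 0.094, about 6% of 1.68.

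**Shift in the mean with no drug effect.** Shift = share × 2.81:
- 10%: 0.28, or 17% of 1.68
- 20%: 0.56, or 33%
- 30%: 0.84, or 50%
- 60% (18 of 30): 1.69, the full planned effect

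**Share needed to reach significance.** Smallest significant mean change = t(0.975, 29 df) × SD/√30, which is 1.20, 0.86 and 0.67 for r = 0, 0.5 and 0.7. As a fraction of 2.81 that is 43%, 30% and 24%. These shares are slightly low, because a mixture of responders and non-responders also widens the SD. The simulation below includes that widening.

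**Chance of a false significant improvement.** 100,000 simulated trials per case, zero drug effect, k of 30 subjects given +2.81, paired t-test at two-sided 0.05. The nominal chance in the favourable direction is 2.5%.

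| Subjects with full gain | r = 0 | r = 0.5 | r = 0.7 |
|---|---|---|---|
| 3 of 30 | 5.8% | 7.6% | 9.0% |
| 6 of 30 | 12.6% | 18.5% | 25.4% |
| 9 of 30 | 23.8% | 37.8% | 51.8% |
| 18 of 30 | 74.0% | 94.3% | 99.3% |

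**Time between clamps.** The first dose follows the baseline assessments by 1 to 4 weeks (Section 2.3.2), and Visit 18 falls on Day 87-92 (Table 1). The interval is therefore (87 − 1)/7 + 1 = 13.3 weeks to (92 − 1)/7 + 4 = 17.0 weeks, before visit windows.

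**The case against.** **The size is an upper bound.** The 2.81 comes from a supervised programme, and Section 1.3.1 says adherence to weight loss and exercise is typically poor. No passage says how many subjects would be dieting or training; a research registry and advertisements do not show that recruits are. A subject already well into a programme has part of the gain in the baseline clamp. All of this stands, so the shares are assumptions and only change after the baseline clamp counts. Duration helps the objection less, since the interval between clamps can approach the programme's 4 months.

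**The problem would be visible.** Body weight, waist and hip, DEXA and maximal exercise testing are all repeated at Week 12. A reader might infer that lifestyle change could never be told apart from drug effect; that goes too far, because substantial weight loss or training would show in these data. But Section 2.6 treats weight, DEXA and fitness only as outcomes, with no sensitivity analysis using them for the clamp result. The dietary recall in Section 2.4.8 is aimed at nitrate and nitrite intake. Adjusting afterwards is also ambiguous, since weight change is a secondary endpoint and may itself be a drug effect.

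**The criterion may already reach this.** It opens with treatments in general and ends open-endedly, so a recently started weight-loss drug is plausibly excluded. The examples named are medications, however, and reading the text to cover diet or training is strained.

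**Instructions could be elsewhere.** The consent pages were not available, so the point is limited to the eligibility lists and visit descriptions.

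**The root cause is the uncontrolled design,** which is openly stated. That is true, and an entry rule cannot stop changes begun later.

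**Conclusion.** The omission is real and should be corrected. As written, the plan admits subjects whose weight or training may be changing, and its primary analysis counts the resulting gain as response to nitrite. If 10-30% of subjects had the full supervised-programme gain, the mean would move by 17-50% of the planned effect, and the false-positive chance would rise from 2.5% to between about 6% and 52%, depending on share and correlation. Those figures rest on assumed shares, an assumed correlation, zero drug effect and SDs borrowed from the diet and exercise data; smaller unsupervised gains would reduce them.

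Three stronger readings are not supported. A reader might infer that one subject changing habits could create the trial's effect; it takes roughly a quarter to two fifths of subjects with the full gain to reach significance, and about 60% to give 1.68. A reader might take falling weight or fat and rising fitness as further hypothesised benefits; the hypothesis in Section 1.2 names no direction for them. A reader might take the training phrase in Section 5.1.2 as evidence of a hidden exercise intervention; nothing in the schedule bears that out, and it is a text conflict to be reconciled.

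Confidence is high in the omission and the direction of the bias, and low in its actual size.

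**What to change.** 1. Add to Section 3.3 and the synopsis an exclusion for current or planned participation in a weight-loss or structured exercise programme, use of weight-loss medication, or weight change in the prior three months above a percentage chosen by the sponsor. Assess it by history at Visit 1, before the baseline clamp and biopsy at Visit 3.
2. Instruct subjects from Visit 1, and again at Visit 4, to keep their usual diet and activity through Week 12. Starting only at Visit 4 would leave the 1 to 4 weeks after the baseline clamp uncovered.
3. Reconcile the reference to training sessions in Section 5.1.2 with the schedule, which contains none.
4. Apply the criterion at entry only. Body weight is an endpoint, so change after dosing should not exclude anyone.

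The cost is an amendment to the eligibility list, one repeated instruction and a text correction, with no new procedure. Expect a few more screen failures and reliance on recalled weight history. Without a control group the bias is reduced, not removed, and the report should say so.

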4. RECRUITMENT AND INFORMED CONSENT PROCEDURES

4.1 RECRUITMENT METHODS

The potential study subjects will be recruited from university and community advertisements and the University of Pittsburgh Nutrition and Obesity Research Center registry.

Potential subjects will also be identified by the physician investigator who is also the primary care or treating physician. The physician investigator who already has knowledge of and access to subjects' information will review the subjects' records to identify potential research subjects for

the study. After identifying potentially eligible subjects, the physician investigator will then approach these subjects to discuss the research opportunity.

To minimize the possibility that subjects will feel obligated to participate, investigators will reinforce with their subjects that participation is voluntary, that they do not have to participate, and the decision not to participate will not affect their care, now or in the future. The physician investigator will also allow subjects to make further inquiries if they are interested.

4.2 INFORMED CONSENT PROCEDURES

Subjects must provide informed consent. The information about this study will be given to the subject in language understandable to them. Either the physician investigator or a non-physician member of the research team will present the study. They will verbally present a general outline of the research plan, including inclusion and exclusion criteria, to the prospective participant. The consent form, outlining the design of the study, will include the risks and benefits of participating, and will be reviewed and the physician investigator and/or non-physician member of the research team will answer any questions. Prospective participants may take as much time as required to make an informed decision. Written informed consent will be obtained from each participant and the investigator prior to performing any research study procedures.

5. POTENTIAL RISKS AND BENEFITS

5.1 POTENTIAL RISKS

5.1.1 Risk of Experimental Drug Intervention

Numerous studies have evaluated acute, subacute and chronic drinking water exposures of nitrite in laboratory animals and drinking water and dietary exposures in humans. Recent studies are available using a high dose of nitrite by oral route in the form of beet root juice. Recent studies have evaluated acute exposures of oral preparations of nitrite on PK and blood pressure and are characterized below. More extensive human data is available on parenteral sodium nitrite as it is currently available and approved by the FDA for use in the emergency treatment of cyanide poisoning^{31,32}. It is also notable that nutraceutical preparations are currently being sold with levels of nitrite (12.7 mg per tablet).

Nitrite:

Sodium nitrite has been used commercially as a food preservative, an anti-corrosive agent, a coloring agent, and an anti-anginal agent, with additional uses in laxatives, burn ointments, and liniments. Amyl nitrite has been inhaled or ingested as an euphoric stimulant. Nitrite has also been found as a contaminant in well water. Literature searches generated case reports of nausea, vomiting, abdominal pain, dizziness, headache, flushing, cyanosis, tachypnea, dyspnea, hypotension and death attributed to excess nitrite (high-dose) exposure from these sources as a consequence of methemoglobinemia due to oxidation of heme-iron in oxyhemoglobin. Normal background methemoglobin production is 1-3%. If levels of methemoglobin rise above approximately 30% of total hemoglobin, a subject may appear cyanotic and experience dyspnea, due to the reduced oxygen carrying capacity of hemoglobin (methemoglobin cannot bind oxygen). Levels above 50% can cause seizures, hypotension, coma and death. Sodium nitrite

administration for cyanide poisoning at the labeled dosage of 300 mg causes methemoglobinemia, a desirable effect, as methemoglobin binds to cyanide, thus protecting cellular mitochondria. A standard dose of nitrite used for cyanide poisoning is 300 mg up to 600 mg. Note that methemoglobin levels have never risen higher than 3% at the currently used therapeutic doses (< 75 mg) in 80 volunteers in phase I studies at the NIH.

The Sponsor of this study proposal, [name], has previously held an IND for sodium nitrite (IND # 70,411) for cardiovascular applications and currently has an approved IND for the use of sodium nitrite for lung transplant recipients (IND # 111,643). The cardiovascular IND involved the administration of sodium nitrite to 69 normal volunteers in 4 phase I-II clinical trials without observed adverse effects. He has also treated 11 subjects with sickle cell disease on this IND without observed adverse effects. The lower doses of nitrite used in these investigational treatment regimens – 60-120mg daily or 20-40% of the dose (300mg) used in the emergency treatment of cyanide poisoning – do not produce methemoglobin levels greater than 3% and have not been associated with clinically significant hypotension. There have been no adverse events noted in the 80 treated normal human volunteers and patients with sickle cell disease disease³³⁻³⁵. In another study by Gladwin et al., 18 healthy adults received an infusion of sodium nitrite totaling 75 mg (15 minutes each x 2 infusions). This was associated with a 7 mmHg decrease in mean arterial pressure, a peak methemoglobin of less 3% and no other significant effects³⁴. Note this single dose is 1.9 times the single dose per time of day we plan to use in this trial.

In an open-label three-way crossover study, 9 healthy adult subjects received two single high dose oral sodium nitrite aqueous solutions (0.12 and 0.06 mmol NaNO₂/mmol Hb, equivalent to 290-380 mg and 140-190 mg sodium nitrite, respectively, depending on the total body hemoglobin level of the person) and one intravenous sodium nitrite dose (0.12 mmol NaNO₂/mmol Hb)¹⁸. Note that this is 1.2-3.2 times the daily dose we plan to use in this trial. There was a washout period of at least 7 days between each of the treatments. Mild headache occurred in 44-55% of subjects and was the most frequent complaint during each treatment session, which the authors ascribed to the sodium nitrite, not methemoglobinemia, as the percentage of methemoglobinemia stayed below clinically toxic levels (<15%). By report, up to 22% experienced nausea, which subsided within half an hour¹⁸. The pharmacokinetic analysis of this study indicated similar bioavailability of oral and IV delivery of nitrite, as well as similar side effect and safety profiles.

A recent study determined the safety and feasibility of prolonged intravenous nitrite infusion. Twelve adult volunteers received increasing starting doses of sodium nitrite, 4.2 to 533.8 µg/kg/hr for 48 hours. Dose limiting toxicity occurred at 445.7 µg/kg/hr (10.6 mg/kg/day) and was limited to asymptomatic transient decreases of arterial blood pressure of up to 20 mmHg and asymptomatic increases of methemoglobin levels above 5%. No tolerance or clinically significant rebound was observed³⁶. Note, this is 8.2 times the daily dose we plan to use in this trial (based on an adult body weight of 95 kg).

For nitrite, two retrospective case-control studies have shown that high maternal dietary nitrite intake from cured meat or drinking water during pregnancy might be associated with risk of childhood brain tumors and possibly gastric and esophageal cancer. This evidence is only based on retrospective case-control studies; cohort studies have found no significantly increased risks²⁴.

In the 2001 National Toxicology Program (NTP) Report summarizing 2-year rodent drinking water studies, there was no evidence of carcinogenic activity of sodium nitrite in male or female F344/N rats exposed to up to 130 mg/kg/day in males and 150 mg/kg/day in females, or in male B6C3F1 mice exposed to up to 220 mg/kg/day. There was equivocal evidence of carcinogenic activity of

sodium nitrite in the highest dose of 165 mg/kg/day in female B6C3F1 mice based on the positive trend in the incidences of squamous cell papilloma or carcinoma (combined) of the forestomach. Exposure to sodium nitrite in drinking water resulted in increased incidences of epithelial hyperplasia in the forestomach. However, no chromosomal damage (genetic toxicity) was observed in three studies conducted in rats and mice *in vivo*³⁷. Taken together, these findings suggest minimal carcinogenic nitrite-mediated risk.

In the current study, we will use much lower doses of nitrite than used safely in any of these studies. Our nitrite dose of 20 mg three times daily stepping up to 40 mg three times daily is lower than the dose used on the cardiovascular IND and <40% of the dose for cyanide poisoning.

To summarize, we anticipate the following symptoms by organ system and likely frequency of risk:

Gastrointestinal

- Common: none
- Frequent: none
- Infrequent: dry mouth
- Rare: nausea, abdominal pain, and vomiting

Hematologic

- Common: none
- Frequent: none
- Rare: methemoglobinemia

Cardiovascular

- Common: none
- Frequent: none
- Rare: flushing, tachycardia, hypotension

Neurologic

- Common: none
- Frequent: none
- Rare: headache, dizziness, seizure, coma

Respiratory

- Common: none
- Frequent: none
- Rare: tachypnea, dyspnea, cyanosis

